## 6. STATISTICAL METHODOLOGY

## 6.1 Statistical and Analytical Issues

## 6.1.1 Statistical Methods

For quantitative variables, descriptive statistics will include the number of subjects (n), mean, standard deviation (SD), median, minimum and maximum. Categorical variables will be summarized using the number (n) and percentage (%) of subjects for each category. Unless otherwise specified, the denominator for all percentages will be the number of subjects in the respective treatment group who have data for the respective time point in the applied analysis population. Percentage change from baseline will be calculated using the non-missing (see section 6.1.2) data of both baseline and the respective post-baseline value.

The primary efficacy analyses will only include efficacy data that were captured in the eDiary for hot flashes which were treated with study drug (VERU-944 or placebo). All baseline measurements for efficacy will be collected prior to dosing in the treatment period. By default the frequency and severity of hot flashes at baseline will be determined from the second week of the first two weeks of hot flash eDiary that were recorded; If a patient qualified for the study entry by number of hot flashes during the second week of screening, then data from that week will be used as their baseline. However, if a patient did not qualify for study entry based on the number of hot flashes during that second week then data from the screening week that was used to qualify the patient will be used as their baseline instead. Percentage change from baseline is defined as the post-baseline value of interest minus the baseline value then divided by the baseline value and finally converted to a percentage by multiplying by 100.

A 1-sided alpha level equal to 0.10 will be used to determine statistical significance for the primary and secondary efficacy objectives related to hot flash frequency and severity.

For the treatment period, baseline for the safety assessments will be defined as the Day 1 assessment, or if missing, the last assessment prior to dosing.

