## Adjustment for Multiple Comparisons

The Hochberg procedure will be applied to control for multiplicity for each of the primary and secondary hot flash related endpoints. Each endpoint will have 4 analyses associated with them to account for the two active dose arms (10 mg and 50 mg) each compared to baseline by two methods each (MMRM test for slope and MMRM test for change from baseline at the specified week). These may be referred to as sets of analyses. Hochberg is a step-up procedure based on univariate p-values. This procedure begins

with the least significant p-value and then examines the other p-values in sequential order, making alpha level adjustments along the way, until a significant p-value is observed. Once achieved, all following lower p-values in the sequence would be considered significant. For example, if one has 4 hypotheses the following will be performed:

- Step 1: Order the p-values from largest (least significant) to smallest (most significant)
- Step 2: Using the pre-specified overall alpha level,  $\alpha_0=0.10$ , one-sided, compare the largest p-value, P1, to the overall alpha level. If P1<0.10 then all (null) hypotheses are rejected; otherwise go to step 3.
- Step 3: Compare the second largest p-value, P2, to  $\alpha_1$ =0.10/2=0.05. If P2<0.05 then this and all further hypotheses are rejected; otherwise repeat for the third, P3, and fourth, P4, largest p-values compared with  $\alpha_2$ =0.10/3=0.033 and  $\alpha_3$ =0.10/4=0.025 as necessary to either reject all remaining hypotheses or conclude no significant difference exists.

For this study, during Stage 1, Hochberg's procedure will rank the p-values from highest to lowest for each statistical test within each set of analyses: 10 mg versus placebo slope difference (through Week 6), 50 mg versus placebo slope difference (through Week 6), 10 mg versus placebo mean difference at week 6, 50 mg versus placebo mean difference at Week 6. Adjustment for the single comparison of 100 mg versus placebo in Stage 2 will be necessary only for the two MMRM modes, means and slopes.

Overall, for the multiple tests of primary and secondary endpoint analyses alpha control will be achieved by a gate-keeping method such that the endpoints are ordered and the preceding endpoint must be shown to be significant in order for endpoints down the list to be eligible for significance.

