#### Common analytical methods for all hot flash related analyses

The MMRM analyses shown in the following section with SAS code written specifically to address the primary analysis of difference in percentage change of the frequency of hot flashes at Week 6 between each of the active arms and placebo are the **SAME** for all hot flash related analyses, both frequency and severity, at all weeks of interest. Simple changes to the data set to subset to the appropriate weeks of data and to the LSESTIMATE statements are all that is necessary to construct the appropriate tests. MMRM models that test for MEAN difference between active arm(s) at Week 6 and placebo and separately for a

difference in SLOPE between active arm(s) at Week 6 and placebo. There is no plan to compare the active arms to each other.

If the MMRM models does not converge or have poor fit, T-tests or non-parametric tests, if the data are deemed non-normally distributed, will compare percentage changes over time between (T-test or Wilcoxon rank sum test) each active arm and the placebo arm, respectively.

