## 6.3.1.1 Primary Efficacy Endpoint Analysis (Hot Flash Frequency at Week 6)

STAGE 1:

The primary frequency efficacy endpoint is percentage change in frequency of moderate and severe hot flashes (vasomotor symptoms) from the baseline week to Week 6 (Day 42). The statistical tests for significant differences with regards to the percentage change between placebo and each of the active arms, 10 mg 50mg, and perhaps 100 mg comprise the main tests of interest.

The SAS code for performing the MMRM analyses to test for a significant difference in the MEAN percentage change in frequency of moderate to severe hot flashes between each of the dose arms and placebo evaluated at Week 6 (primary analysis week) is shown below. Note that this analysis will generate two of the four tests that are part of the primary analysis to which the Hochberg procedure will apply.

PROC MIXED DATA= XXX; CLASS subjid tx week; MODEL cfb = tx week\_2 tx\*week\_2; REPEATED week / type=AR(1) sub=subjid(tx); LSESTIMATE tx\*week '10MG VS Placebo at Week 6' [1, 10 6] [-1, P 6]; LSESTIMATE tx\*week '50MG VS Placebo at Week 6' [1, 50 6] [-1, P 6]; WHERE week le 6; RUN;

The variables used in the above model will be defined as follows: tx=treatment; week (1, 2... 6); cbf=change from baseline value, week\_2=week (week will be treated as a categorical variable in the class statement and week\_2 will be treated as a continuous variable in the model... effectively the values of these variables will be an exact match). By creating week\_2 in a preceding data step, this allows for LESTIMATES to be computed at a specific WEEK (treated as categorical in the CLASS statement) but allows week to be treated as a continuous variable, WEEK\_2 in the model.

This model will be run 3 separate times using 3 separate covariance structures to determine best fit. The same model will be run, with the following specified change on the REPEATED line: (1) type=AR(1); (2) type=CS; and (3) type=UN. If a model does not converge, then disregard that model. If more than 1 model remains, then refer to the Akaike's Information Criteria (AIC) score to determine model fit. The best fit model will be chosen as having the AIC value closest to zero. The model type chosen will be referenced in the footnote for each model output.

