Additional prespecified analysis of the data will be conducted regardless of whether the MMRM model(s) converge, and will be considered the definitive tests for significance in the event the MMRM model(s) do not converge:

• T-tests will be generated to compare the percentage change from baseline to each of Week 6 in the placebo arm to each of the 10 mg and 50 mg arms. If the data are determined to be non-normally distributed then the Wilcoxon rank sum test will be the definitive test of significance.

• Wilcoxon rank sum tests will be generated to compare the percentage change from baseline to Week 6 in the placebo arm to each of the 10 mg and 50 mg arms.

The SAS code for performing the MMRM analyses to test for a significant difference in the SLOPES of the percentage change in frequency of moderate to severe hot flashes between each of the dose arms and placebo by Week 6 (primary analysis week) is shown below. Note that these analyses will generate the remaining two of the four tests that are part of the primary analysis to which the Hochberg procedure will apply.

The where statement in PROC MIXED has been used to simplify the interpretation of the output so that one model will be run for the 10 mg versus placebo slope analysis and a separate one for the 50 mg versus placebo slope analysis through Week 6. Variable have the same meaning as defined in the above analysis.

PROC MIXED DATA=XXX; CLASS subjid tx; MODEL cfb= tx week tx\*week / s; RANDOM intercept week/ type=AR(1) sub=subjid g; WHERE tx in (10, P) and week le 6; /\* repeat for 'tx in (50, P)' \*/ RUN;

This model allows for both the intercept and the slope to differ randomly for each subject but the overall p-value for the interaction term is interpreted as a test of the slope between the stated active arm and placebo. Note, if the p-value is significant, the estimated coefficients must be in the appropriate direction to conclude the result is in favor of the active dose arm.

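### The means MMRM picks its covariance by AIC with no small-sample correction, so the Week 6 standard error is wrong, in either direction, when variance changes moderately over weeks

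*SAP*

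**What the plan says.** SAP 6.3.1.1 fits the means model to percentage change in weekly frequency, with arm-specific linear trends over Weeks 1-6 and a contrast with placebo at Week 6. On the covariance it says "This model will be run 3 separate times using 3 separate covariance structures to determine best fit", namely "1) type=AR(1); (2) type=CS; and (3) type=UN". Structures that fail to converge are dropped. Among the rest, "The best fit model will be chosen as having the AIC value closest to zero". The printed REPEATED line carries only TYPE= and SUB=. No DDFM=KR, EMPIRICAL or GROUP= option appears, so the standard errors are model-based.

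The slope test in the same section uses a different covariance: "This model allows for both the intercept and the slope to differ randomly for each subject".

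The means code is reused for every other hot flash endpoint and week ("Simple changes to the data set to subset to the appropriate weeks of data", SAP 6.3.1, common analytical methods) and for Stage 2. On the error level, SAP 6.1.1 says "A 1-sided alpha level equal to 0.10 will be used to determine statistical significance". Under the multiple-comparison rule, "Each endpoint will have 4 analyses associated with them" in Stage 1, with Hochberg steps from 0.10 down to 0.025. Stage 2 uses 0.10 and 0.05.

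A t-test and a Wilcoxon test at Week 6 are always run, but they decide only if the MMRM does not converge (SAP 6.3.1 adds poor fit).

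**The concern.** AR(1) and CS estimate one variance for all six weeks. If the variance at Week 6 differs from the average over weeks, the standard error of the Week 6 contrast is off by about the square root of that ratio. UN avoids this but costs many more parameters, so AIC can leave AR(1) or CS in place when the variance change is moderate. When UN is chosen, its standard error still treats the estimated covariance as known, which understates uncertainty at 30 men per arm. At stake are the standard error, interval and p-value of the primary comparison and, by the same code, of every hot flash secondary endpoint.

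**Working it through.** **Inputs from the documents.** One-sided alpha is 0.10 (SAP 6.1.1). There are about 30 men per arm, with three arms in Stage 1 and two in Stage 2 (SAP 3). The structures, selection rule and linear week term come from SAP 6.3.1.1. The interim efficacy population requires six weeks of hot flash data (SAP 5), so Weeks 1-6 are taken as complete.

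**Not in the documents, so assumed.** SD by week, correlation between weeks and the degrees-of-freedom method. The sample-size paragraph (SAP 6.1.4) does not help: it sets the variance equal to an active-arm mean that is not stated.

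**The plan's own figures.** The Hochberg levels reproduce: 0.10/1, 0.10/2, 0.10/3 and 0.10/4 give 0.10, 0.05, 0.033 and 0.025.

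**AIC penalty.** UN over T weeks has T(T+1)/2 parameters: 6×7/2 = 21 at six weeks and 12×13/2 = 78 at twelve. AR(1) and CS have 2. At six weeks UN must therefore improve −2 log-likelihood by more than 2×(21−2) = 38 to be chosen.

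**Hand check of direction and size.** Assume the SD rises linearly from 1 to 1.25 over six weeks. The weekly variances are 1, 1.1025, 1.21, 1.3225, 1.44 and 1.5625, with mean 1.273. A pooled-variance standard error at Week 6 is then √(1.273/1.5625) = 0.903 of the true one. The normal cut-off 1.282 becomes 1.157 (tail 0.124), and 1.960 becomes 1.769 (tail 0.038). If the SD falls to 0.8, the mean variance is 0.815, the ratio is √(0.815/0.64) = 1.128 and the tail at nominal 0.10 is 0.074. This ignores selection of UN and the linear week term, so it only bounds what follows.

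**Simulation of the SAP rule.** REML fits of all three structures, lowest AIC chosen, linear week, model-based standard error, between-within degrees of freedom. There were 6,000 null trials per scenario, so the simulation error is √(0.1×0.9/6000) = 0.004 at 0.10 and 0.002 at 0.025. Lowest AIC equals AIC closest to zero while AIC is positive, which it was in all runs on the percentage scale. Results for 3×30, over AR(1)-type and CS-type truths:

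| SD ratio, Week 6 to Week 1 | Error at 0.10 | Error at 0.025 | Structure chosen |
|---|---|---|---|
| 0.67 | 0.096-0.104 | 0.025-0.027 | |
| 0.8 | 0.081-0.090 | 0.017-0.020 | |
| 1.0 | 0.099-0.100 | 0.024 | UN in about 1% |
| 1.25 | 0.116-0.119 | 0.035-0.036 | AR(1) or CS in 83-90% |
| 1.5 | 0.114-0.123 | 0.034-0.038 | |
| 2.0 | 0.109-0.110 | 0.029-0.031 | UN in about 100% |

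For 2×30 the maxima were 0.127 at 0.10 and 0.073 at 0.05. With 22 per arm in three arms (an assumed smaller evaluable set) they were 0.128 at 0.10 and 0.042 at 0.025. A repeat simulation with the SD rising 25-50% gave 0.115-0.120 at 0.10 and 0.030-0.038 at 0.025 for 3×30, and 0.110-0.131 at 0.10 and 0.064-0.074 at 0.05 for 2×30. It gave 0.096-0.101 at 0.10 under constant variance and 0.077-0.091 under falling variance.

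**What remains when UN is chosen.** Kenward-Roger enlarges the variance of the UN Week 6 contrast by 9% (3×30) and 14% (2×30). Leaving it out makes the 3×30 standard error too small by a factor of √1.092 = 1.045, which by normal tails gives 0.110 at 0.10 and 0.030 at 0.025. Simulated UN without correction gave 0.029-0.033 at 0.025.

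**Family-wise error.** Hochberg was applied to all tests in the set, with the slope test approximated by a t-test on subject slopes. Stage 1 gave 0.082-0.102 and Stage 2 gave 0.092-0.108.

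**After the fix.** UN with Kenward-Roger (2,500 trials per scenario; 3×30, 3×22 and 2×30) gave 0.096-0.109 at 0.10, 0.046-0.056 at 0.05, 0.030-0.037 at 0.033 and 0.022-0.028 at 0.025. That is nominal within simulation error (0.006 at 0.10 and 0.003 at 0.025).

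**The case against.** The strongest reply is that the effect is conditional and small where decisions are made. The documents give no SD by week. A reader might infer that the Week 6 test simply rejects too often; the documents do not support that, since it is nominal under constant variance and conservative under moderately falling variance. This stands.

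Rising variance is plausible but not shown. In the slope model, the coded random intercept and slope share a variance s² with correlation r, so the variance at week t is s²(1 + 2rt + t²) plus residual. Its derivative, 2s²(t + r), is positive from Week 1 on. In 15 of 16 simulated count scenarios the SD ratio was 1.06-1.98; one was flat at 0.99. The first is a modelling choice and the second rests on assumed inputs. Nor do the two models contradict each other, as a reader might infer: UN is among the candidates and allows variance to change by week.

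A reader might also infer that the harm is greatest at the strict Hochberg steps. That is true only as a ratio: for 3×30, 0.038/0.025 = 1.5 against 0.123/0.10 = 1.2. In absolute terms the excess is 1.3 points at 0.025 and 2.3 points at 0.10.

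Nor does the excess carry through to a large risk of calling an inactive dose effective, because Hochberg has slack with positively correlated tests. That slack does not repair the reported intervals and per-test p-values. Stage 2 also does not follow mechanically from significance: the sponsor may, but need not, withhold it (SAP 6.7).

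Finally, the rule is prespecified, the chosen structure is footnoted, and the parallel t-test and Wilcoxon test would expose a discrepancy. They do not override a converged MMRM.

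**Conclusion.** The point holds as one about the validity of the Week 6 standard errors, intervals and per-test p-values. If the SD rises by 25-50% over Weeks 1-6, one-sided per-test error is about 0.11-0.12 at 0.10 and 0.03-0.04 at 0.025 in Stage 1, and about 0.11-0.13 at 0.10 and 0.06-0.07 at 0.05 in Stage 2. If variance falls moderately, the test is conservative, at about 0.08-0.09 for nominal 0.10. If variance is constant, the AIC-selected test is nominal. If variance changes strongly, AIC tends to choose UN, and any remaining excess comes from the uncorrected UN standard error. Family-wise error stays at approximately 0.08-0.11.

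These figures rest on assumed SDs and correlations, complete Week 1-6 data, 30 men per arm and between-within degrees of freedom. They apply to Week 6; no error rate is claimed for the other weeks. The change is a cheap improvement rather than the repair of a serious error.

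**What to change.** Delete the three-way AIC selection from SAP 6.3.1.1. Prespecify one covariance model, TYPE=UN with DDFM=KR, and name a fixed order of heterogeneous structures (for example TOEPH, then ARH(1), then CSH) to be used, first to converge, if UN does not. The fallback is more likely to be needed for the Week 12 endpoints, where UN has 78 covariance parameters; its error rate was not simulated. Apply the rule to all hot flash endpoints and both stages, and state it in SAP 6.3.1 with the common methods.

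The cost is SAP wording and one PROC MIXED option. The 9% (3×30) to 14% (2×30) larger variance makes standard errors about 4% to 7% larger than uncorrected UN (√1.09 = 1.04, √1.14 = 1.07). Intervals are slightly wider and power slightly lower; the power loss was not computed.

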## STAGE 2:

The analyses conducted in Stage 2 will be the exact same as in Stage 1, except the 10 mg and 50 mg dose of study drug will be replaced with a 100 mg dose of study drug. A separate and distinct placebo group will be used for Stage 2. The Hochberg procedure will have to address only two multiple comparisons, i.e., the MMRM slope models and the MMRM means models as there is now only one dose level comparison to placebo. The two alpha levels that may be needed to assess significance will be only  $\alpha_0=0.10$  and possibly  $\alpha_1=0.05$ . Here is the appropriate code for the LSESTIMATE statement.

LSESTIMATE tx\*week '100MG VS Placebo at Week 6' [1,100 6] [-1, P 6];

Also, as a reminder, the SAS code shown for the primary analysis can be used in this second stage as well for its primary analysis of hot flash frequency as well as for all secondary hot flash related endpoints.

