#### 6.7 Interim Analysis

During Stage 1, after the last subject has completed the Day 42 visit, an unblinded interim analysis (IA) of the Week 6 (Day 42) hot flash primary endpoint (frequency) and first secondary endpoint (severity) of VERU-944 will be conducted. A blinded analysis of the safety will also be conducted. Both the Sponsor and CRO study team will remain blinded to patient level data until completion of the study stage. An

unblinded statistical support group, independent of the study team (within the CRO), along with a representative of Veru Inc., will review the IA results and determine steps forward. It is of note that due to the material nature of the IA results of this study in the business of Veru Inc., a publicly traded company, these results may be required to be released in a press release prior to the completion of Stage 1 of this study.

The analyses to be included in the IA will be the analyses of hot flash frequency at Week 6 (Section 6.3.1.1) and the hot flash severity at Week 6. These analyses will include the summary statistics and MMRM model for both the ITT and EEIA populations. The sensitivity analyses associated with these sections will not be conducted during the IA.

In addition to the efficacy analyses, a blinded safety report will be reviewed to assess drug safety. All IA analyses will be conducted on the EEIA population.

If an effective dose of VERU-944 is achieved in Stage 1, as defined as a statistically significant result), the Sponsor reserves the right to not initiate Stage 2 of the protocol. However, if an effective dose is not achieved in the Stage 1 IA, then the study will commence with Stage 2.

Regardless of IA outcome, unless safety issues are observed, the Stage 1 section of the study will continue to completion at 12 Weeks with Follow-up.

Assuming Stage 2 is implemented, an additional replicate IA will be conducted after the last subject in Stage 2 has completed the Day 42 visit. This IA will follow the same procedures as done for Stage 1.

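### The SAP sets a one-sided 0.10 level, but tests slopes with a directionless p-value and never says how one-sided p-values are obtained before Hochberg

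*SAP*

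**What the plan says.** - **Level.** SAP 6.1.1: "A 1-sided alpha level equal to 0.10 will be used to determine statistical significance for the primary and secondary efficacy objectives". This covers the hot flash endpoints. SAP 6.3.1 (Adjustment for Multiple Comparisons) repeats one-sided 0.10 inside the Hochberg steps.
- **Family.** In Stage 1, "Each endpoint will have 4 analyses associated with them to account for the two active dose arms" and the two methods (means and slope). The cut-offs are 0.10, 0.05, 0.033 and 0.025. In Stage 2, "The Hochberg procedure will have to address only two multiple comparisons, i.e., the MMRM slope models and the MMRM means models", with cut-offs 0.10 and 0.05.
- **Slope tests (SAP 6.3.1.1).** "the overall p-value for the interaction term is interpreted as a test of the slope between the stated active arm and placebo". The next sentence adds the direction rule: "if the p-value is significant, the estimated coefficients must be in the appropriate direction to conclude the result is in favor" of the active arm.
- **Means tests (SAP 6.3.1.1).** The contrast is coded in the form "10MG VS Placebo at Week 6' [1, 10 6] [-1, P 6" and closed with a bracket. It requests no tail, and the text gives neither a conversion nor a direction rule.
- **Fallback tests (SAP 6.3.1.1).** The t-test and the Wilcoxon rank sum test are named without a side.
- **Use of the result.** SAP 6.7: "If an effective dose of VERU-944 is achieved in Stage 1, as defined as a statistically significant result", the sponsor may choose not to start Stage 2; if none is achieved, Stage 2 goes ahead. The gatekeeping rule in SAP 6.3.1 also turns on significance alone.

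**The concern.** The cut-offs are one-sided, but the only p-value that the SAP describes in words is directionless. The sign check in SAP 6.3.1.1 is needed only because that p-value does not carry the sign. Ranking such p-values against one-sided cut-offs has two effects:

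1. Each affected test runs at half its stated level, which costs power.
2. Direction is checked only after significance. A small p-value from a dose that does worse than placebo therefore enters the ranking as if it were evidence of benefit, and it can change the cut-off that applies to the other dose.

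The Stage 1 result decides whether an effective dose has been found and bears on whether Stage 2 starts. The same code is reused for every hot flash endpoint and for Stage 2. The outcome should not depend on whether a programmer halves some p-values, all of them or none.

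**Working it through.** **Inputs.** One-sided alpha 0.10 and power 0.90 (Protocol 9.1, SAP 6.1.4); Hochberg cut-offs (SAP 6.3.1); four tests in Stage 1 and two in Stage 2.

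**The plan's own figure.** Let m be the placebo mean, with difference 0.4m and variance 0.6m (the active-arm mean):

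n per arm = 2(1.2816 + 1.2816)² × 0.6m / (0.4m)² = 2 × 6.569 × 3.75 / m = 49.3/m.

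The documents do not give m. If m = 12/7 = 1.71 per day (an assumption, from the entry minimum of 12 per week), n = 29, and power at n = 30 is 0.909. Exactly 30 needs m = 1.64. If m = 12 per week, n = 5. So 30 per arm cannot be confirmed from the documents, and I take the stated 0.90 as given. The noncentrality is then 1.2816 + 1.2816 = 2.563.

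**Level per test.** Each slope model contains two arms and continuous week, so the interaction has one degree of freedom. Under the null, P(two-sided p < a and favourable sign) = a/2. The cut-offs 0.10, 0.05, 0.033 and 0.025 act as one-sided 0.05, 0.025, 0.0167 and 0.0125.

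**Power per test.** With a one-sided p-value, power = Φ(2.563 − z₁₋ₐ). With an unconverted two-sided p-value plus sign check, it is Φ(2.563 − z₁₋ₐ/₂).

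| Cut-off a | One-sided p | Two-sided p | Loss (points) |
|---|---|---|---|
| 0.10 | Φ(2.563 − 1.282) = 0.900 | Φ(2.563 − 1.645) = 0.821 | 7.9 |
| 0.05 | 0.821 | Φ(2.563 − 1.960) = 0.727 | 9.4 |
| 0.033 | 0.767 | 0.668 | 9.9 |
| 0.025 | 0.727 | Φ(2.563 − 2.241) = 0.626 | 10.1 |

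**Full Hochberg procedure, all p-values unconverted.** Simulation with 1,000,000 draws. The two doses are correlated 0.5 through the shared placebo arm; the correlation between the means and slope tests is assumed, at 0, 0.5, 0.8 and 0.95. Ranges run over those four values. Entries are the probability of at least one favourable rejection.

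| Stage 1 scenario | One-sided p | Two-sided p | Loss (points) |
|---|---|---|---|
| No effect (family error) | 0.066–0.090 | 0.033–0.047 | – |
| Both doses, both tests | 0.915–0.985 | 0.846–0.958 | 2.7–6.9 |
| 50 mg only, both tests | 0.777–0.928 | 0.687–0.864 | 6.3–9.0 |
| 50 mg only, means test only | 0.729–0.740 | 0.629–0.638 | about 10 |
| 50 mg only, means plus half-size slope effect | 0.727–0.799 | 0.628–0.694 | 10.0–10.5 |

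In Stage 2 the null family error is 0.083–0.100 with one-sided and 0.041–0.053 with two-sided p-values. With no effect in Stage 1 and no direction rule applied, at least one test rejects in the harmful direction with probability 0.033–0.047; counting the means tests alone, 0.024–0.029.

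**Two cases to check by hand.** In each, every dose has the same two-sided p-value for its means and slope tests.

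*A missed benefit.* 50 mg favourable, 0.04 and 0.04; 10 mg favourable, 0.50 and 0.50.
- None converted: 0.50 > 0.10, 0.50 > 0.05, 0.04 > 0.033, 0.04 > 0.025. Nothing is significant.
- All converted: 0.25, 0.25, 0.02, 0.02. The third, 0.02, is below 0.033, so both 50 mg tests are significant.
- Only the means converted: 0.50, 0.25, 0.04, 0.02. Only the last passes (0.02 < 0.025), so only the 50 mg means test is significant.

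The same data give three different results.

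*Help from an adverse result.* 10 mg worse than placebo, 0.04 and 0.04; 50 mg favourable, 0.09 and 0.09.
- None converted: the largest, 0.09, is below 0.10. All four are rejected and 50 mg passes.
- All converted: 10 mg becomes 1 − 0.02 = 0.98 twice, and 50 mg becomes 0.045 twice. Then 0.98 > 0.10, 0.98 > 0.05, 0.045 > 0.033 and 0.045 > 0.025. Nothing is significant.

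**The case against.** The strongest reply is that the SAP says one-sided twice, in 6.1.1 and in the Hochberg steps, so a careful programmer would convert. The printed code is visibly a template: the data set is a placeholder, the change variable is spelled two ways, and the means contrast names a treatment-by-week effect that its MODEL statement replaces with the continuous version. A missing option in such code is weak evidence of what will be run. This stands for the means and fallback tests, where two-sided input is inferred from silence and from an assumed software default. It does not answer the slope tests, where the SAP names the directionless p-value and puts the sign check after significance.

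A reader might infer that a dose worse than placebo could be declared effective. For the slope tests the direction rule prevents that. For the rest, a one-sided level implies a direction even though none is written, SAP 6.7 speaks of an effective dose, an unblinded group with a sponsor representative reviews the result, and not starting Stage 2 is an option rather than an automatic step. What remains is a wording gap and the effect on the ranking.

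A reader might also take 8 to 10 points as the trial's loss of power. That is per test at a fixed cut-off; the procedure-level loss depends on the scenario. The 0.90 benchmark is itself loose. It was set for one comparison of mean frequency at Week 4, and even with correct one-sided p-values the strictest Hochberg step leaves 0.727. Converting the p-values does not restore 0.90.

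**Conclusion.** The mismatch is real and worth correcting before the Day 42 data are unblinded. Taken as written, the two Stage 1 slope tests run at exactly half the stated one-sided level. If the means p-values are also left unconverted, so do all four, with a per-test loss of 7.9 to 10.1 points and a loss of about 3 to 10.5 points in the chance of at least one favourable rejection. Favourable-direction family error in Stage 1 is then about 0.03–0.05 rather than 0.07–0.09. Claims of benefit are therefore not inflated overall, and the main cost is missed benefit. The exception is the ranking: an adverse result at one dose can relax the cut-off for the other.

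The per-test figures assume the stated 0.90 power and normal test statistics. The procedure-level figures also assume the 0.5 dose correlation and the range of means–slope correlations, with every p-value unconverted. The case in which only the slope p-values stay two-sided was not simulated. The documents do not say that two-sided p-values enter Hochberg for all four tests, and they do not support a claim that a harmful dose would be called effective.

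**What to change.** - **SAP 6.3.1, Adjustment for Multiple Comparisons.** State that every p-value entering Hochberg, for means, slope and fallback tests in both stages, is one-sided for a greater reduction than placebo. It is p/2 if the estimate favours VERU-944 and 1 − p/2 otherwise, where p is two-sided, and it is computed before ranking.
- **SAP 6.3.1.1.** Replace the after-the-fact sign check for slopes with a reference to that rule.
- **Gatekeeping rule (SAP 6.3.1) and effective-dose definition (SAP 6.7).** Add that significance means significance in favour of VERU-944.

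One-sided options in the SAS statements are an alternative way to do the same thing and need not be prescribed. The cost is a few lines of SAP text, with no new data and no change to sample size. In the simulations, Stage 1 family error after the change is 0.066–0.090, within the stated 0.10.
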